2.9 Sample size calculation

The study does not include formal statistical hypothesis testing and the sample size (N=20) is not derived based on power considerations.

A response rate of 10% or less is considered as an insufficient level of activity for the proposed patient population. With a sample size of 20 patients, there is an approximately 58.4% chance that the exact 95% CI will exclude an insufficient response rate of 10% when the true ORR is 30%. The probability increases to 75.5% and 87.4%, when the true ORRs are 35% and 40%, respectively. For an observed response rate of 30.0% (6 responders in 20 patients), the exact 95% CI is (11.9%, 54.3%). The operating characteristics of this study are summarized in [Table 2-5](#).

Table 2-5 Operating characteristics for various ORRs when N=20 patients

True ORR	Probability that exact 95% CI excludes an insufficient level of 10% *	Expected number of responders	Observed ORR and exact 95% CI
30%	58.4%	6	30.0% (11.9%, 54.3%)
35%	75.5%	7	35.0% (15.4%, 59.2%)
40%	87.4%	8	40.0% (19.1%, 63.9%)

*Of 20 patients at least 6 responders are required to meet the criteria (i.e., exact 95% CI excludes an insufficient level of 10%), thus it is calculated as a binomial probability that $\geq 6/20$ responders are observed given the true ORR.

2.10 Power for analysis of key secondary variables

Not applicable.

2.11 Interim analysis

No interim analysis is planned in this study.

3 Changes to protocol specified analyses

No changes are made.

4 Additional details on implementation of statistical methodology

The sections below contain additional details on statistical methodology that will be included in Appendix 16.1.9 (Documentation of Statistical Methods) of the CSR as well as rules details on programming rules that will be followed to implement the analyses described in [Section 2](#).

4.1 Data included in the analyses

This section provides additional details to those included in [Section 2.1](#).

Each analysis (primary analysis of study data after all patients have either completed at least 6 cycles of treatment or discontinued earlier; final analysis of study data once at least 75% of patients have died) will include the data with an assessment date or event start date (e.g., vital sign assessment date or start date of an AE) prior to or on the analysis cut-off date. For example, if the cut-off date is 30DEC2008, an AE starting on 28DEC2008 will be reported, whereas an AE starting on 31DEC2008 will not be reported.

4.2 Patient classification into analysis sets

This section provides additional details to those included in [Section 2.2](#).

Patients are excluded from the analysis sets based on the protocol deviations entered in the database and/or on specific patient classification rules as shown in [Table 4-1](#) below.

Table 4-1 Patient classification rules

Analysis set	Protocol deviation ID* leading to exclusion	Additional patient classification rules leading to exclusion
Full Analysis Set	INCL13 (Patients who do not provide the written informed consent prior to any screening procedures), TRT02 (Patients who do not receive at least one dose of study drug without the withdrawal of informed consent after continuing into the treatment phase)	
Safety Set	INCL13, TRT02	

*Protocol deviation IDs are from the 'PD Specs and Edit Checks' sheet of Study Specification Document (SSD) final version 1.0. If the SSD (protocol deviation IDs) is updated during the study, refer to the corresponding IDs provided in the latest SSD at the time of analysis.

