13. Written informed consent must be obtained prior to any screening procedures. If consent cannot be expressed in writing, it must be formally documented and witnessed, ideally via an independent trusted witness.

14. Willingness and ability to comply with scheduled visits, treatment plans, laboratory tests and other study procedures.

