7.2.1.1 Baseline imaging (+/- photography) assessment

Imaging assessments will be performed at screening/baseline Day -28 to Day -1 prior to Cycle 1 Day 1.

Any imaging assessments already completed during the regular work-up of the patient within 28 days prior to start of treatment, including before signing the main study ICF, can be considered as the baseline images for this study.

Any imaging assessments obtained after first dose of study drug cannot be considered baseline images. The following assessments are required at screening/baseline:

- CT with IV contrast or MRI of chest and abdomen
- Whole body bone scan
- Brain CT with IV contrast or MRI scan
- Additional CT scan or MRI of other metastatic sites (e.g., neck, pelvis, etc.)
- Localized bone CT scan, MRI or x-ray (for any lesions identified on whole body bone scan not visible on chest/abdomen (and pelvis if applicable) CT scan or MRI)

- Photography (for any skin lesions) if clinically significant

If a patient is known to have a contraindication to CT intravenous (IV) contrast media or develops a contraindication during the trial, a non-contrast CT of the chest (MRI is not recommended due to respiratory artifacts, however if CT is not feasible per local regulations, MRI can be performed instead) plus a contrast-enhanced MRI (if possible) of the abdomen and pelvis (as applicable) should be performed.

A whole body bone scan should be performed per institutional standard of care for all patients to detect any skeletal metastases present [e.g., Tc-99 bone scan, whole body bone MRI, FDG-PET or sodium fluoride positron emission tomography (NaF PET)]. Localized CT, MRI or X-rays should be acquired for all skeletal lesions identified on the screening bone scan, which are not visible on the chest, abdomen and pelvis CT/MRI.

If clinically indicated, CT or MRI of other areas (neck, pelvis) of disease as appropriate should be performed.

Color photography, including a metric ruler to estimate the size of the lesion, must be acquired for all skin lesions present per instructions provided in the photography manual from the designated vendor.

Chest x-ray and ultrasound should not be used for lesion evaluation in this study.

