10.1 Analysis sets

10.1.1 Full Analysis Set

The Full Analysis Set (FAS) will include all patients who receive at least one dose of LDK378. The FAS will be used for summaries of baseline characteristics and all efficacy analyses, unless otherwise specified.

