2.2 Analysis sets

[figure not shown]
A patient is considered to be enrolled into the study if they have signed informed consent. Only patients who have signed informed consent will be included in the analysis sets.

Full Analysis Set

The Full Analysis Set (FAS) will include all patients who receive at least one dose of LDK378. The FAS will be used for summaries of baseline characteristics and all efficacy analyses, unless otherwise specified.

Safety Set

The Safety Set will include all patients who receive at least one dose of LDK378. All safety data will be analyzed using the Safety Set. In this non-randomized study the FAS and Safety Set are identical.

Frequency counts and percentages (using FAS as denominator) of patients in each of the above defined analysis sets will be summarized. In addition, a listing of patients included in each of the analysis sets will be provided.

[Section 4.2](#) provides further details regarding the derivation the analysis sets.

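### Read literally, SAP Table 4-1 drops a dosed patient whose consent was signed late from both the FAS and the Safety Set, although both sets are defined to include every dosed patient

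*SAP*

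**What the plan says.** Protocol 10.1.1 states: "The Full Analysis Set (FAS) will include all patients who receive at least one dose of LDK378". Protocol 10.1.2 defines the Safety Set the same way and says the two sets are identical. Neither section has a consent condition.

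SAP 2.2 repeats both definitions, for example "The Safety Set will include all patients who receive at least one dose of LDK378", and adds one condition: "Only patients who have signed informed consent will be included in the analysis sets". It does not say when consent must have been signed.

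SAP 4.2, offered as further detail on SAP 2.2, says: "Patients are excluded from the analysis sets based on the protocol deviations entered in the database and/or on specific patient classification rules". Table 4-1 then lists two deviation codes for the FAS and the same two for the Safety Set:

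- "INCL13 (Patients who do not provide the written informed consent prior to any screening procedures"
- TRT02, which concerns patients who enter the treatment phase but receive no dose.

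The INCL13 label follows inclusion criterion 13 in Protocol 5.2: "Written informed consent must be obtained prior to any screening procedures". That criterion also accepts consent that cannot be given in writing, if it is documented and witnessed.

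SAP Section 3, on changes to the protocol-specified analyses, reads: "No changes are made".

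**The concern.** Having signed consent and having signed it before the first screening procedure are different conditions. SAP 2.2 asks for the first; Table 4-1, as worded, enforces the second. Table 4-1 is the rule a programmer would implement, so the narrower condition would govern.

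The safety side matters most. A consent-timing breach says nothing about exposure, yet it would remove an exposed patient's adverse events, laboratory data and ECGs from every summary. The same patient would leave the primary response analysis, where each patient counts in a trial of about 20.

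**Working it through.** **Step 1. Apply each text to one hypothetical patient**, who signs consent after the first study-specific screening procedure and then receives at least one dose.

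| Source | Condition for inclusion | Result |
|---|---|---|
| Protocol 10.1.1, 10.1.2 | at least one dose | in both sets |
| SAP 2.2 | at least one dose, consent signed | in both sets |
| SAP 4.2, Table 4-1 | neither INCL13 nor TRT02 | out of both sets (INCL13) |

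TRT02 agrees with the definitions, so the conflict lies in INCL13 alone. Read literally, INCL13 also catches a patient whose consent was documented and witnessed rather than written, which criterion 13 accepts.

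**Step 2. Trace where that patient would be reported.**

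- Primary and secondary efficacy: FAS (SAP 2.7.2, 2.8.1). Absent.
- Safety: Safety Set (SAP 2.8.2). Absent.
- Exposure and concomitant therapy: Safety Set (SAP 2.6). Absent.
- Disposition: FAS (SAP 2.5). Absent.
- Protocol deviations, tables and listing: FAS (SAP 2.4). Absent, so the INCL13 breach itself is not shown.
- Analysis-set summary: percentages use the FAS as denominator (SAP 2.2), so the exclusion would not show there.
- Screen-failure listing: for patients not treated (SAP 2.3). Does not apply.

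The count of all screened patients in SAP 2.3 would still include the patient. Protocol Section 12 requires significant deviations to be reported in the CSR.

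**Step 3. Reproduce the plan's figures.** Inputs from SAP 2.9 are N = 20, an insufficient rate of 10%, and at least 6 responders needed. For x responders of n, the Clopper-Pearson limits are:

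- lower = 2.5% quantile of Beta(x, n − x + 1)
- upper = 97.5% quantile of Beta(x + 1, n − x)

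For 6/20 this gives 11.9% to 54.3%, as stated. P(X ≥ 6 | n = 20) is 58.4%, 75.5% and 87.4% at true rates of 30%, 35% and 40%, as stated.

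**Step 4. Remove one patient from 6/20.**

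| Removed | Result | Exact 95% CI | Shift |
|---|---|---|---|
| none | 6/20 = 30.0% | 11.9 to 54.3 | |
| one responder | 5/19 = 26.3% | 9.1 to 51.2 | 26.3 − 30.0 = −3.7 points |
| one non-responder | 6/19 = 31.6% | 12.6 to 56.6 | 31.6 − 30.0 = +1.6 points |

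**Step 5. Chance that the interval excludes 10%.** Assume one or two patients are removed, independently of response. Six responders are still needed, because the lower limits for 5/19 (9.1%) and 5/18 (9.7%) are below 10%.

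| N analysed | True 30% | True 35% | True 40% |
|---|---|---|---|
| 20 | 58.4% | 75.5% | 87.4% |
| 19 | 52.6% | 70.3% | 83.7% |
| 18 | 46.6% | 64.5% | 79.1% |

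**The case against.** The best defence is that INCL13 merely implements the signed-consent condition. SAP 4.2 presents itself as detail on SAP 2.2, the code takes its number from inclusion criterion 13, and its full specification is in a Study Specification Document that is not among the documents. Table 4-1 never mentions late consent. This stands as a statement about possible intent. It does not remove the conflict, because the wording in the table covers late consent.

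The event is also unlikely. The consent date is captured in the CRF (Protocol 11.3), monitors verify consent in full (Protocol 9.2), and the sponsor approves entry after consent is signed (Protocol 7.1.1.1). That stands too: the effect is conditional.

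Starting from 6/20 shows the most sensitive case. From 7/20, losing a responder gives 6/19, whose interval still excludes 10%. No hypothesis test is planned, so no formal decision turns on that limit.

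Two stronger readings are tempting, and the documents do not support them.

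- A reader might infer that permitted pre-consent imaging would trigger INCL13. Protocol 7.2.1.1 says routine work-up scans, "including before signing the main study ICF, can be considered as the baseline images for this study". Protocol 7.1.1 and 11.3 require consent before study-specific procedures. A routine scan of this kind is therefore no breach and should not be coded as one.
- A reader might infer a route for removing patients once their outcome is known. Outcomes are visible in an open-label trial, but the rule is written in advance, rests on recorded dates, and deviations are finalised before database lock (SAP 2.4). Little discretion is left.

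**Conclusion.** The inconsistency is real and should be corrected. As worded, Table 4-1 excludes a dosed late-consenter whom Protocol 10.1.1, Protocol 10.1.2 and SAP 2.2 include, and SAP Section 3 does not declare the difference. The more serious consequence is for safety reporting: an exposed patient's safety data, and the deviation itself, would have no place in the planned tables.

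The effect on the primary endpoint is a few points per patient: −3.7 or +1.6 from 6/20. A reader might take the shift to be one patient's share of 20. It is not, because the denominator falls as well. At a true rate of 30%, the chance of excluding 10% would fall from 58.4% to 52.6% with one removal.

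These sizes assume one or two removals, and the documents give no count of INCL13 deviations. If none occurs, nothing changes. The conclusion rests on the literal wording of Table 4-1. It does not establish that the sponsor means to exclude late-consenters.

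**What to change.** In Table 4-1, for both sets:

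- Replace INCL13 with a condition that no signed, or formally documented and witnessed, informed consent was ever obtained.
- Keep TRT02.
- State that dosed patients whose consent was late stay in the FAS and the Safety Set.
- Report INCL13 timing breaches as CSR-reportable deviations. With these patients in the FAS, the tables in SAP 2.4 pick them up without further change.

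Whether consent was ever obtained is a matter of record, so the condition needs no judgement about how late is too late. Bring the Study Specification Document into line, since Table 4-1 takes its codes from there.

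If the sponsor does intend to exclude late-consenters, the alternative is to declare this in SAP Section 3 and say where their safety data and deviations will be reported.

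The cost is a small wording change to Table 4-1. With all dosed patients kept, the operating characteristics in SAP 2.9 stand as printed.

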4.3 Last contact date

The last contact date is used for censoring in OS analyses and will be derived for patients not known to have died at the analysis cut-off date using the latest complete date among the following:

CONFIDENTIAL - For Business Use Only

- All patient assessment dates (e.g., blood draws, vital signs, performance status, ECG, tumor assessments).
- Start and end dates of antineoplastic therapies administered after study drug discontinuation.
- AE start and end dates.
- From the [Survival information] eCRF page,
 - Last known date subject alive if answer to question 'Is subject alive?' is 'Lost to follow-up';
 - Date of assessment if answer to question 'Is subject alive?' is Yes;
 - Note: If answer to question 'Is subject alive?' is 'Unknown', neither last known date subject alive nor date of assessment is used.
- Study drug start and end dates.
- Date of discontinuation collected on the [End of Treatment Phase Disposition] and/or the [End of Post Treatment Phase Disposition] eCRF pages.

Only dates associated with patient visits or actual examinations of the patient will be used in the derivation. Dates associated with a technical operation unrelated to patient status such as the date a blood sample was processed will not be used. Assessment dates after the analysis cut-off date will not be applied to the last contact date.

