7.1 Study flow and visit schedule

Table 7-1 lists all of the assessments and indicates with an “X” the visits when they are performed. Each treatment cycle is 28 days (the 28 days cycle length is fixed regardless of whether the dose of LDK378 is withheld). All visits are to be scheduled according to the appropriate number of calendar days from Cycle 1 Day 1 of study drug administration. A visit window of +/- 1 day in Cycle 1 and +/- 3 days in Cycle 2 onwards is allowed. Imaging evaluations may be performed +/-7 days of the due date of the assessment.

Note: If treatment with LDK378 is withheld at any time during the study, all study visits, safety and efficacy assessments should continue according to the appropriate number of calendar days from Cycle 1 Day 1 as per the schedule of assessments.

All data obtained from these assessments must be supported in the patients’ source documentation. No eCRF will be used as a source document. The table indicates which assessments produce data to be entered into the database (D) or remain in the source documents only (S).

Visit name	Category	Protocol Section	Screening Phase	Treatment Phase				Post treatment follow up phase			Survival follow-up phase
				Cycle 1 (28 d)		Subsequent cycles (28 d)	End of study Treatment (EOT)	30-day safety follow-up	Tumor follow- up if no PD at the EOT	Study phase completion	
Screening Visit (Day -28 to Day -1)				Cycle 1 Day 1	Cycle 1 Day 15	Day 1	End of treatment visit				
Antineoplastic therapies since discontinuation of study treatment	D	7.1.5.3.						X	X		X Every 12 weeks
Survival assessment	D	7.1.5.3.									X Every 12 weeks

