7.1.5.3 Survival follow-up

All patients who had PD as per investigator assessment, have started a new anti-neoplastic therapy, and/or withdrew consent from further study assessments will subsequently be followed for survival information every 12 weeks until death, lost to follow-up or withdrawal of consent for survival follow-up. The investigator or his designee will collect this survival information and any new anti-neoplastic therapies for all patients until the final survival analysis.

Follow-up can be done via a phone contact. Antineoplastic therapies will be captured on the 'Antineoplastic therapies since discontinuation of study treatment' eCRF page following the last dose of the study treatment.

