2.1 Data analysis

Data will be analyzed by Novartis Oncology Biostatistics and Statistical Programming personnel according to the data analysis section 10 of the CLDK378A1201 protocol, which will be available in Appendix 16.1.1 of the CSR. Important information is given in the following sections and details are provided, as applicable, in Section 4 from which Appendix 16.1.9 of the CSR will be extracted.

SAS® version 9.4 (or later version if available at time of database lock) will be used in all analyses.

Data from all patients who signed informed consent in centers that participate in this study will be combined and used in the analysis. Data collected after withdrawal of informed consent will not be reported. Due to expected small size of enrollment at individual centers, no center effect will be assessed. Each analysis will use all data in the database up to the analysis cut-off date, determined prior to database lock.

The analysis cut-off date for the primary analysis of study data will be around 168 days after the first dose of study drug for the last patient enrolled corresponding to when all patients have either completed at least 6 cycles of treatment, i.e., 168 days (1 cycle = 28 days), or discontinued earlier. The results from primary analysis will be reported in the primary (interim) CSR. Following the primary analysis time point, the study will remain open. Patients still being followed on the study will continue as per the schedule of assessments. The analysis cut-off date for the final analysis of study data will be established at the end of the study when at least 75% of deaths have occurred. The results from final analysis will be reported in the final CSR. Note that the analysis cut-off date and reporting strategy may be changed according to the development and/or NDA submission status of LDK378.

[Section 4.1](#) provides further details regarding data to be included in the analyses.

General presentation of descriptive summaries

Qualitative data (e.g., gender, race) will be summarized by frequency counts and percentages. Percentages will be calculated using the number of patients in the relevant population or subgroup as the denominator.

Continuous data (e.g., age, body weight) will be summarized by appropriate descriptive statistics (i.e., mean, standard deviation, median, minimum, and maximum).

Subgroup analysis

Key efficacy endpoints (best overall response, ORR, and DCR) will be summarized for the following subgroups:

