If a patient has not progressed or is not known to have died at the date of analysis cut-off or has received any further anticancer therapy in the absence of disease progression, PFS will be censored at the date of last adequate tumor assessment before the earlier of the cut-off date or the start date of new anticancer therapy. Clinical deterioration will not be considered as a qualifying event for progression. Refer to [Table 2-2](#) for censoring and event date options and outcomes for PFS.

In particular, PFS will be censored at the last adequate tumor assessment if one of the following occurs: absence of event; the event occurred after a new anticancer therapy is given; the event occurred after two or more missing tumor assessments (see [Section 4.7.1](#)). See also [Section 4.6.1](#) describing the special case of a missing baseline tumor assessment.

PFS will be described in tabular and graphical format using Kaplan-Meier methods as described for DOR, including estimated median (in months) with 95% CI, 25th and 75th percentiles with 95% CIs, and Kaplan-Meier estimated probabilities with corresponding 95% CIs at several time points (including at least 4, 8, 12, 15 and 18 months). Censoring reasons will also be summarized.

In addition, the supportive analysis of PFS with censoring rule modified by ignoring further anticancer therapy ('F' in [Table 2-2](#)) will be considered when the percentage of patients censored due to the initiation of new anticancer therapy in the main analysis (for censoring reason classification, see [Section 4.7.1](#)) is equal to or more than 25% of the FAS (i.e., ≥ 5 out of 20 patients). In this supportive analysis, data from tumor assessments performed after the start of further anticancer therapy will also contribute to the determination of censoring and event date for PFS. Except for further anticancer therapy, the same censoring rule used for the main analysis will be followed. PFS will be described in a similar way, as needed.

Overall survival

Overall survival (OS) is defined as the time from the start date of study drug to the date of death due to any cause. If a patient is alive at the date of the analysis cut-off or lost to follow-

up, OS will be censored at the last contact date prior to the cut-off date (see [Section 4.3](#) for further details on derivation of last contact date).

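### The OS censoring rule drops survival shown after the cut-off, while deaths reported between cut-off and lock appear to count; if they do, OS at the primary analysis is modestly too low

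*SAP*

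**What the plan says.** - **SAP 2.8.1, Overall survival.** A patient alive at the cut-off and a patient lost to follow-up are treated alike: "OS will be censored at the last contact date prior to the cut-off date".
- **SAP 4.3.** The last contact date "will be derived for patients not known to have died at the analysis cut-off date using the latest complete date among the following". The sources are assessments, adverse-event dates, later therapy, the survival page, study-drug dates and discontinuation dates, limited to dates of visits or actual examinations. The section ends: "Assessment dates after the analysis cut-off date will not be applied to the last contact date". No sentence moves a patient known to be alive after the cut-off up to the cut-off.
- **SAP 4.1.** Each analysis "will include the data with an assessment date or event start date" on or before the cut-off. In its example, with a cut-off of 30DEC2008, an adverse event that began on 28DEC2008 is in and one that began on 31DEC2008 is out. The date of reporting plays no part.
- **SAP 2.1.** "Each analysis will use all data in the database up to the analysis cut-off date, determined prior to database lock". The time from cut-off to lock is not given.
- **Protocol 7.1.5.3.** After progression, new therapy or withdrawal from study assessments, patients are "followed for survival information every 12 weeks until death, lost to follow-up or withdrawal of consent for survival follow-up". On drug, Protocol 7.1 ties visits to cycles: "Each treatment cycle is 28 days".

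**The concern.** Take a patient in 12-weekly survival follow-up whose next contact falls shortly after the cut-off and before lock. If that contact reveals a death dated before the cut-off, the SAP 4.1 date rule makes it an OS event. If the same contact finds the patient alive, SAP 4.3 ignores it and the patient is censored at the previous contact, up to 12 weeks before the cut-off. Time at risk in that interval is removed only from patients who did not die in it. Censoring then depends on outcome, and the Kaplan-Meier curve is pulled down.

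The effect would be largest at the primary analysis, about 168 days after the last patient's first dose, when more patients are alive and censored than at the final analysis. SAP 2.8.1 reports the OS median and estimates at 4, 8, 12, 15 and 18 months with confidence intervals, so an avoidable shift in these would appear in the study report.

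**Working it through.** The plan gives no sample size, event count or power for OS, so there is no planned OS figure to reproduce. Its only operating characteristics concern ORR and do not bear on this point.

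**1. Inputs from the documents.** N = 20; visits every 28 days on drug; survival contact every 84 days afterwards; primary cut-off 168 days after the last first dose (168/30.4375 = 5.5 months); final cut-off at 75% dead (15 of 20).

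**2. Assumptions not in the documents.** Exponential OS with median m between 8 and 24 months; uniform accrual over 12 to 24 months; no loss to follow-up; median time before the switch to 12-weekly contact of 6 to 6.93 months (the upper value is the median PFS of patients with a prior ALK inhibitor in Protocol 1.2.1.2.2).

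**3. Length of the interval.** On 12-weekly contact it is at most 84/30.4375 = 2.8 months and averages about half that, 1.4 months. On drug it is at most 28/30.4375 = 0.9 months. In simulation at the primary analysis, 0.4 to 0.7 deaths per 20 patients fall within it.

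**4. Rules compared.** Let T be time to death, F the time from first dose to cut-off, and L the last contact at or before F.
- SAP rule with late-reported deaths counted: event at T if T ≤ F; otherwise censored at L.
- Cut-off rule: event at T if T ≤ F; otherwise censored at F.
- Symmetric rule: a death counts only if learned at a contact on or before the cut-off; otherwise the patient is censored at the last contact.
- Truth: S(t) = 0.5^(t/m).

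**5. Primary analysis, 18-month accrual, all late deaths captured before lock.**

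| Median OS (months) | Time (months) | SAP rule | Cut-off rule | Symmetric | Truth |
|---|---|---|---|---|---|
| 12 | 12 | 48.5% | 49.9% | 50.0% | 50.0% |
| 12 | 18 | 32.6% | 35.5% | 35.6% | 35.4% |
| 18 | 12 | 61.7% | 62.9% | 62.9% | 63.0% |
| 18 | 18 | 47.2% | 50.0% | 49.9% | 50.0% |

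The SAP rule falls 1.2 to 1.4 points below the cut-off rule at 12 months and 2.8 to 2.9 points below at 18 months. The cut-off and symmetric rules both recover the truth, so the asymmetry is the cause. The estimated median is about 11.6 against 12.0 months (true 12) and 16.8 against about 18 (true 18).

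**6. Dependence on the cut-off-to-lock lag.** Here a death counts only if the contact that reveals it falls before lock. Accrual is 18 months, median OS 12 or 18 months, and median time on drug 6 months:

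| Lag (days) | Shortfall at 12 months (points) | Shortfall at 18 months (points) |
|---|---|---|
| 0 | about 0 | about 0 |
| 14 | 0.5–0.6 | 1.0–1.2 |
| 28 | 0.9–1.1 | 1.8–2.0 |
| 84 | 1.4–1.7 | 3.0–3.4 |

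**7. Other settings, late deaths captured.** Over 18 to 24 months' accrual and medians of 8 to 24 months, the shortfall is about 0.7 to 1.4 points at 12 months and 1.4 to 2.9 at 18 months. With 12-month accrual it is 1.9 to 2.6 points at 12 months. The 18-month estimate then lies beyond the maximum follow-up (12 + 5.5 = 17.5 months) and is not interpretable.

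**8. Final analysis.** The median moves by 0.03 months or less. The 12-month estimate is 0 to 0.9 points low (1.2 if every survivor is on 12-weekly contact). The 18-month estimate is 0 to 2.3 points low, with the largest values at an assumed median of 8 months.

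**The case against.** **The asymmetry is inferred.** No sentence says that a death counts whenever it is learned of. SAP 4.1 is a general date rule illustrated with vital signs and adverse events, and the SAP 4.3 phrase about patients not known to have died could mean knowledge held on the cut-off day. On that reading both sides stop at the same information and the bias vanishes, as the symmetric rule shows. This stands as a limit on certainty. The date-based wording of SAP 4.1 makes the other reading the more natural one, and the SAP leaves the choice open.

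**The size depends on a lag the SAP does not give.** This stands. The figures near 1.5 and 3 points need about 12 weeks between cut-off and lock, or prompt death reporting.

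**Real contact is denser than modelled.** Patients off drug without progression are scanned every 8 weeks (Protocol 7.1.5.2), there is a 30-day safety contact, and adverse-event and later-therapy dates count. SAP 4.9.7 sets the last dosing date of some ongoing patients to the cut-off; whether that imputed date qualifies under SAP 4.3 is unclear. These can shrink the effect but do not remove it for patients in survival follow-up.

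**The SAP follows the protocol.** Protocol 10.5.2 also censors at last contact. But Protocol Appendix 2 (15.1.25) defines that as the last date the patient was known alive. For someone known alive later, truncating at the cut-off gives the cut-off date.

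**Materiality.** With 20 patients the sampling standard deviation of the Kaplan-Meier estimate was about 12 to 13 points at 12 months and 16 to 17 at 18 months, far larger than the shift. This stands.

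**Conclusion.** The point holds in a conditional and modest form. If deaths dated on or before the cut-off and reported before lock are counted, the censoring rule biases OS downward at the primary analysis. With 18-month accrual and median OS of 12 to 18 months, both assumed, the shortfall at 12 and 18 months runs from about zero with no lag to about 1.5 and 3 points with a 12-week lag. At the final analysis the median is essentially unchanged.

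Three stronger readings may tempt a reader, and the documents support none of them:
- *The SAP states that late-reported deaths count.* It does not; this follows only from combining SAP 4.1 with SAP 2.1.
- *The rule separately inflates the OS gap time in SAP 2.8.1.* Gap time for patients still followed is defined as the distance from censoring to cut-off, so it measures this interval by design. It does not correct OS for it either.
- *A trial conclusion is at risk.* OS is a descriptive secondary endpoint, SAP 2.7.2 plans no hypothesis test, and ORR is untouched.

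A correction is still worthwhile because the error is systematic, avoidable and cheap to remove.

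**What to change.** 1. In SAP 4.3, add: *If a contact, assessment or death dated after the analysis cut-off shows the patient was alive at the cut-off, OS is censored at the cut-off date.* Deaths after the cut-off belong in the sentence because those patients were equally alive at it. Patients with no such evidence stay censored at their last contact.
2. Add the matching exception to the OS paragraph of SAP 2.8.1 and to SAP 4.1, since both now exclude use of post-cut-off information.
3. State that deaths dated on or before the cut-off and reported before database lock count as OS events.

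The cost is a few SAP sentences and minor programming. It makes limited use of survival-status data dated after the cut-off and needs no new data collection.
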